There is substantial experimental evidence, biological rationale, and supportive clinical evidence to suggest the efficacy of the PHARLAP ventilation strategy in ARDS. However, mostly because of concern that SRM's and high PEEP may cause barotrauma and haemodynamic instability in critically ill patients, previous trials may have been sub-optimally designed to determine the true efficacy of such an OLS. The PHARLAP strategy is more intensive, more individual patient tailored and at least as safe as previously studied open lung strategies. In addition, the PHARLAP strategy can be delivered by almost any clinician using any conventional mechanical ventilator and if proven effective and safe, would be highly applicable for widespread use (including the developing world). Given the significance and cost of ARDS, the possible benefits of this strategy, the growing number of recommendations for the use of a LRM with elevated levels of PEEP^{18,19,46}, this study is an important undertaking. The trial will determine whether the PHARLAP ventilation strategy is effective in increasing ventilator free days in patients with ARDS. If the PHARLAP strategy is proven to improve ventilator free days it will provide a strong impetus to conduct an international phase III RCT to determine the effects of this strategy on mortality.

OBJECTIVES

Aim

To determine the efficacy of the PHARLAP strategy compared to a control ventilation strategy in increasing ventilator free days assessed during the 28 days post randomisation.

Hypothesis

The PHARLAP strategy group will have a higher number of ventilator free days at day 28 than the control group.

STUDY OUTCOME MEASURES

Primary outcome

- Number of ventilator free days at day 28 post randomisation

Secondary outcome

- Physiological outcomes:
 - PaO₂/FiO₂ ratio
 - Static lung compliance
- Inflammatory outcomes:
 - Baseline to day 3 change in IL-8 and IL-6 concentrations in broncho-alveolar lavage fluid
 - Baseline to day 3 change in IL-8 and IL-6 concentrations in plasma
- Clinical/patient-centred efficacy outcomes:
 - Use of rescue therapies for severe hypoxaemia – inhaled nitric oxide, inhaled prostacyclin, prone positioning, high frequency oscillatory ventilation and extracorporeal membrane oxygenation (ECMO)
 - Incidence of acute kidney injury (AKI)
 - ICU and hospital length of stay
 - Quality of life assessment (SF-36v2 and EQ-5D) at 6 months
 - Mortality at ICU/hospital discharge, 28 days, 90 days and 6 months

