Site personnel will enrol patients using an internet-based system hosted by the ANZIC Research Centre. Randomisation to either the PHARLAP group or the control group will be by permuted blocks and stratified for centre and for the cause of ARDS (direct or indirect)⁴⁸.

Co-enrolment

Co-enrolment of patients into other interventional studies will be decided by the PHARLAP and the co-enrolling study management committees on a case-by-case basis. Participants can be co-enrolled in observational studies.

PARTICIPATING STUDY SITES

To be confirmed

- Albury Wodonga Health
- CVICU, Auckland City Hospital
- DCCM, Auckland City Hospital
- Austin Hospital
- Barwon Health (Geelong Hospital)
- Flinders Medical Centre
- John Hunter Hospital
- King Abdulaziz Medical City for National Guard (Riyadh)
- Lyell McEwin Hospital
- Middlemore Hospital
- Nepean Hospital
- Northern Hospital
- Launceston
- Prince Charles Hospital
- Royal North Shore
- Royal Prince Alfred
- St Vincents Hospital (Dublin)
- The Alfred Hospital
- Wellington Hospital
- Wollongong Hospital

STUDY PROCEDURES

Commencement of mechanical ventilation strategy

Patients in both groups should be commenced on the assigned mechanical ventilation strategy as soon as possible (but no later than 4 hours) after randomisation.

Prior to changing the pre-randomisation mechanical ventilation settings to the assigned strategy, 3 tasks need to occur in the following order in both groups of patients:

1. Predicted body weight should be estimated.
2. Static respiratory compliance should be measured (see below).
3. Specimens of blood and BAL should be collected (see below) – after static respiratory compliance has been measured.

Estimation of predicted body weight:

Before setting up the ventilator strategy, the patient's predicted body weight must be determined. This should be estimated using a formula which requires height⁴⁹ (Appendix 1). If there has been no recent (last few days) measurement of height, the height should be estimated using a formula which requires measurement of the demi-arm span (Appendix 1).

Measurement of static respiratory compliance:

- The patient should be adequately sedated (no spontaneous breaths).
- An expiratory pause of 5 seconds should be set to measure intrinsic PEEP (PEEPi). If the 5 second pause can not be achieved (because the next breath occurs before the end of the pause), a shorter pause should be set.
- Total PEEP is calculated as PEEPi + set PEEP.

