The site principal investigator will be responsible to ensure that all conditions for approval of the study are met and that amendments to the protocol or serious adverse events are also reported to the Human Research Ethics Committee (HREC, or equivalent) as required.

This protocol will also be submitted to the Guardianship Board or similar where this is necessary for legal surrogates to provide informed consent for patient participation. The site principal investigator will be responsible to obtain such approval from the relevant body prior to obtaining legal surrogate consent.

DATA MANAGEMENT

Data collection methods

All study-related data will be collected by trained staff at each study site using a paper source document (case report form) developed by the coordinating centre. Data will then be entered into an internet-based database designed by the CIDMU. Data queries will be automatically generated as they are entered into this database.

Enrolled patients will be followed up to death or 6 months post-enrolment. Data collection will be restricted primarily to those variables necessary to define clinical patient characteristics including: baseline demographics, primary diagnoses, physiological parameters, diagnostic interventions, therapeutic interventions and documentation of deaths, other serious adverse events, and patient outcomes.

Patients and/or their legal surrogate will be asked to provide three possible points of contact (home and close family contact details) to the research staff prior to discharge. Full protocol data will be collected in all patients including those where the study is discontinued prior to the end of the study period. Patients (or a surrogate – generally a close family member) who are alive at 6 months after enrolment will be asked to complete a questionnaire via post or telephone by a trained follow-up assessor from the coordinating centre. This follow-up assessor will use a standardized structured telephone questionnaire⁵² to measure the QOL assessments EQ-5D⁵³ and SF-36v2^{54,55}.

Data variables collected

- Demographic data
- Height
- Weight
- Admission diagnosis
- Cause of ARDS
- Classification of ARDS as diffuse or focal (by an independent radiologist)
- PaO₂/FiO₂ ratio at enrolment
- Barotrauma
- Mode of ventilation
- Ventilation parameters
- ABG results
- Vital signs
- SOFA scores
- Daily fluid balance
- Rescue therapy details
- Co-interventions
- Open lung procedure details
- Ventilation weaning

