A protocol deviation is an unanticipated or unintentional departure from the expected conduct of an approved study that is not consistent with the current research protocol or consent document. A protocol deviation may be an omission, addition or change in any procedure described in the protocol.

Given that investigators are responsible for patient safety and care, they may implement a deviation from, or a change of, the protocol to deal with an immediate hazard to trial patients without prior HREC approval. The implemented deviation or change must be reported in a protocol deviation form. The deviation must be reported by the principal investigator using the case report form so that it can be reported to the coordinating centre and the HREC (if applicable).

STATISTICAL CONSIDERATIONS

Power calculations and sample size

Based on data from the PHARLAP pilot study, with 282 subjects this study will have an 80% power to detect a difference equal to 33% of a standard deviation (equal to 3VFD's) with a two sided p-value of 0.05. To account for likely occurrence that VFD will not follow a normal distribution, the sample size has been inflated by 15% to 324 in accordance with Lehmann⁵⁶. Allowing for up to a 5% rate for withdrawal or loss to long term follow up, 340 patients will be enrolled.

Statistical and analytical plan

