Independent senior statisticians at Monash University will perform data analysis. Baseline and outcome variables will be compared using Chi-square tests for categorical variables, Student's t-test for normally distributed continuous variables and Wilcoxon rank-sum tests for non-normally distributed continuous variables. Duration of ventilation will be analysed using Cox-Proportional Hazards regression with deceased patients censored at death, allowing for results to be reported using Kaplan Meier curves. Furthermore, duration of ventilation will be stratified into survivors and non-survivors. If as expected, the duration of ventilation in each strata is well approximated by a log-normal distribution, this will enable log-transformed duration of ventilation to be analysed using parametric analysis (student t-tests) and reported as a ratio (95%CI). If normality cannot be achieved then the data would subsequently be analysed non-parametrically. Should any baseline imbalances be found to exist between groups, additional sensitivity analysis will be performed using Cox Proportional Hazards regression adjusting for imbalanced covariates. All analyses will be intention-to-treat. A complete statistical analysis plan will be finalised prior to study completion.

Interim analysis

One midpoint interim analysis (after primary outcome data is available for 170 patients) will be performed to assess accumulated safety data. This will be reported to the Data Safety Monitoring Committee, but will not be made available to the Management Committee or to study sites.

Subgroup analyses

We plan to compare study outcomes in the following pre-specified subgroups:

- (a) Patients with severe ARDS ($\text{PaO}_2/\text{FiO}_2 < 100$) versus patients with moderate ARDS ($\text{PaO}_2/\text{FiO}_2$ 100-200 mmHg) at enrolment.
- (b) Patients with diffuse ARDS versus patients with focal ARDS at enrolment (determined by independent radiologists).
- (c) Patients who are responders to the open lung strategy versus patients who are non-responders (defined as meeting lack of improvement in static lung compliance definition).

SAFETY OF SUBJECTS

Data Safety Monitoring Committee

An independent Data Safety Monitoring Committee, comprising experts in clinical trials, biostatistics and intensive care will be established. The committee will be responsible for monitoring mortality related to serious adverse events, serious adverse events and reviewing the interim safety analysis.

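### Static compliance and PaO₂/FiO₂ are compared with unadjusted tests at no stated time point, although a baseline value of each is collected and could be used for precision

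*Combined protocol and SAP*

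**What the plan says.** **Method.** Under Statistical and analytical plan, the protocol states that "Baseline and outcome variables will be compared using Chi-square tests for categorical variables". That sentence continues with the t-test for normally distributed continuous variables and the Wilcoxon rank-sum test for the others. The only covariate adjustment in the section is a Cox regression. It is a sensitivity analysis, and it is triggered only if baseline imbalance is seen. The section also promises a complete SAP before the study ends; that plan is not among the documents.

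**Outcomes.** Under Secondary outcome, the physiological outcomes are the PaO₂/FiO₂ ratio and "Static lung compliance". Neither has a day, a change score or a summary measure. The IL-6 and IL-8 outcomes in the same list are defined as change from baseline to day 3.

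**Data available.**
- Data variables collected includes "PaO₂/FiO₂ ratio at enrolment".
- Commencement of mechanical ventilation strategy lists, for both groups and before the assigned strategy starts, "Static respiratory compliance should be measured (see below").
- The two sections on specific measurements on day 3 require compliance again in both groups. Appendix 3 agrees: compliance on day 1 and day 3 only.
- Appendix 3 schedules ventilation observations daily until liberation. Blood gas results are a collected variable, but no frequency is given.

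**The concern.** These two outcomes show most directly whether the strategy opened the lung. A patient's compliance or oxygenation before randomised treatment is likely to predict the later value. A comparison that ignores it leaves explainable variation between patients in the error term, so the confidence interval is wider than the collected data require.

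The missing time point is a separate gap. Without a named day, the SAP writer must choose one later, and a reader cannot tell what the t-test or rank-sum test will be applied to.

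**Working it through.** **1. The plan's own figure.** The only power statement concerns ventilator free days: "with 282 subjects this study will have an 80% power to detect a difference equal to 33% of a standard deviation", "with a two sided p-value of 0.05". With 1:1 allocation (assumed, since no ratio is stated), n per arm = 2 × (1.960 + 0.842)² / d².
- d = 1/3: 142 per arm, 284 in total.
- d = 0.33: 145 per arm, 290 in total.

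Both are within 3% of 282. Next, 282 × 1.15 = 324.3, which matches "the sample size has been inflated by 15% to 324", and 324 × 1.05 = 340.2. So 340 reproduces. It does not depend on how the physiological outcomes are analysed, and no power is stated for them.

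**2. Inputs for the check.** 324 / 2 = 162 patients per arm with complete data. The correlation ρ between baseline and follow-up is not in the documents, so 0.3 to 0.7 is assumed. The same variance at both times, and the same ρ in both arms, are also assumed.

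**3. Formulas.** The variance of the arm difference, relative to a t-test on the follow-up value alone, is:
- follow-up only: 1
- change from baseline: 2(1 − ρ)
- linear model with arm and baseline: 1 − ρ²

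The adjusted model against the change score is therefore (1 − ρ²) / [2(1 − ρ)] = (1 + ρ)/2.

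The difference detectable with 80% power, in SD units, is √(2/162) × 2.802 × √(variance factor).

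**4. Results.**

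| | ρ = 0.3 | ρ = 0.5 | ρ = 0.7 |
|---|---|---|---|
| Variance factor, change score | 1.40 | 1.00 | 0.60 |
| Variance factor, adjusted model | 0.91 | 0.75 | 0.51 |
| Cut against follow-up only | 9% | 25% | 49% |
| Cut against change score | 35% | 25% | 15% |
| Detectable difference, follow-up only | 0.311 | 0.311 | 0.311 |
| Detectable difference, change score | 0.368 | 0.311 | 0.241 |
| Detectable difference, adjusted model | 0.297 | 0.270 | 0.222 |
| 324 patients with adjustment are worth, against follow-up only | 356 | 432 | 635 |

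The cut against follow-up only is ρ², so its exact values are 0.09, 0.25 and 0.49. The figure of 51% at ρ = 0.7 is the variance that remains (1 − 0.49 = 0.51). The exact range of the cut is thus 9% to 49%.

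**5. Reading.** The adjusted model is at least as precise as either unadjusted form at every ρ in the range. Which form it should be judged against cannot be settled from the documents, because the outcome is not defined.

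**The case against.** **The plan is silent rather than opposed.** It does not forbid baseline adjustment, a two-sample test on change from baseline would use the baseline value, and a complete SAP is promised. This stands in part. It is why the gain is shown against both forms. But a change score is written down only for the cytokines, and a later SAP does not alter the method now stated.

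**The correlation is assumed.** This stands. Eligibility also restricts enrolment PaO₂/FiO₂ to below 200 mmHg. Such restriction tends to weaken the correlation with later values, so the upper end of the range is doubtful for that outcome. Incomplete readings also make the gains upper bounds.

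A reader might infer more than the documents support:
- *Daily compliance readings are thrown away.* There are none. Compliance is scheduled only on day 1 and day 3.
- *The comparison is biased by chance baseline differences.* Under randomisation the unadjusted test is unbiased, and its standard error already allows for such differences.
- *Separate daily tests will inflate false positives.* No day-by-day testing is planned; this would be conjecture from a missing time point.
- *A mixed model over a fixed week is an easy main analysis.* Daily blood gases are inferred, not scheduled. Readings stop at death or liberation, which determine the primary outcome and may differ by arm. An averaged effect over fixed days would extrapolate PaO₂/FiO₂ to dead and extubated patients.

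**Conclusion.** The point holds as a loss of precision and a gap in specification for two secondary outcomes. The stated tests use no covariate, a baseline value of each outcome is available, and neither outcome has a time point.

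With complete data and an assumed correlation of 0.3 to 0.7, baseline adjustment reduces variance by ρ², from 9% up to about half (49% by the arithmetic above), against a follow-up-only test. Against a change-score test the reduction runs from 35% down to 15%. These figures are for the t-test; the rank-sum test likewise uses no covariate.

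Nothing here affects the analysis of ventilator free days, the sample size of 340, or the validity of the unadjusted randomised comparison. The case is clearest for day-3 compliance, where both measurements are scheduled in both arms. For PaO₂/FiO₂ it depends on a blood gas being available on the chosen day.

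**What to change.** Amend the Statistical and analytical plan, and carry the change into the SAP:

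1. **Static compliance.** Name day 3 as the time point. Analyse it in a linear model with arm and pre-strategy (day 1) compliance.
2. **PaO₂/FiO₂.** Name one main time point, for example day 3 to match the compliance and cytokine measurements. Analyse it in a linear model with arm and enrolment PaO₂/FiO₂, on the log scale if skewed. A baseline-adjusted repeated-measures model over the ventilated days can be supportive, if the SAP states which reading counts each day and that the result describes patients alive and still ventilated.
3. **Missing readings.** Report by arm how many patients have no reading and why: dead, liberated or not measurable.

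The cost is SAP wording and a little more analysis work. Baseline adjustment does not remove one limitation: both outcomes remain conditional on being alive and ventilated at the time point, so the counts in item 3 belong beside the estimates.

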As PHARLAP proposes to include 340 patients, based on previous studies (2,4,5,8) about one third of patients will fall into each group and this should still leave adequately sized groups of patients with focal, patchy and diffuse to study their influence on the PHARLAP primary outcome of number of ventilator free days at day 28 post randomisation, markers of inflammatory mediators, and several other secondary outcomes. With a total of 300 patients in the study based on data from [name] et al (8) –personal communication we will likely get 80-100 patients per subtype, which would mean approximately 40 to 50 patient in each arm per subgroup. This should give us a reasonable sample size for each subgroup, and whilst mortality differences or VFDs may be unlikely, the potential for differences in other outcomes is reasonable, beside it will generate hypothesis for future studies.

We plan to analyse the outcomes of the study by utilising the general linear model with each outcome primary and secondary outcomes (PHARLAP - primary and secondary outcomes analysed separately as the dependent variable while ventilation strategy (PHARLAP / control), CXR coding (diffuse, focal, patchy) will be entered as independent factors. Interaction between ventilation strategy and the CXR coding will also be studied in the model. Post Hoc analysis will be done between the various CXR and ventilation subgroups (it will compare the outcomes of the CXR subgroups (diffuse, patchy and focal) within and among the PHARLAP and control group).

Funding

Diffuse versus focal substudy is supported by a \$34 950 grant (ANZCA) for procurement of the Chest X rays, cost of independent radiological scoring, statistical advice and salary support for a research assistant based at the ANZIC-RC.

Publications

A separate publication following the main publication will be completed in the name of the PHARLAP investigators led by [name] and the PHARLAP writing committee.

References

1. Nieszkowska A, et al. Incidence and regional distribution of lung over inflation during mechanical ventilation with positive end-expiratory pressure. *Crit Care Med* 2004; 32:1496–1503
2. Puybasset L, et al. Regional distribution of gas and tissue in acute respiratory distress syndrome. III. Consequences for the effects of positive end-expiratory pressure. *Int Car Med* 2000;26:1215-1227

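### Randomisation is stratified by centre and cause of ARDS, but the main plan compares ventilator-free days with an unadjusted test and fixes no covariates in advance

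*Combined protocol and SAP*

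**What the plan says.** - **Enrolment and randomisation:** allocation "will be by permuted blocks and stratified for centre and for the cause of ARDS", the cause being direct or indirect.
- **Statistical and analytical plan:** baseline and outcome variables are compared by chi-square test, Student's t-test or "Wilcoxon rank-sum tests for non-normally distributed continuous variables". Neither stratification factor is mentioned, and no sentence says which test is primary for VFDs.
- **Power calculations and sample size:** the sample is enlarged by 15%, with the reason given as "To account for likely occurrence that VFD will not follow a normal distribution". The Wilcoxon test is therefore evidently the one intended.
- **Adjustment in the main plan:** if baseline imbalances appear, "additional sensitivity analysis will be performed using Cox Proportional Hazards regression adjusting for imbalanced covariates". No outcome, covariate list or criterion for imbalance is given.
- **Appendix 7 (sub-study):** a general linear model covers the primary and secondary outcomes, but "ventilation strategy (PHARLAP / control), CXR coding (diffuse, focal, patchy) will be entered as independent factors". Centre and cause of ARDS are absent.
- **Inflammatory outcomes:** these are defined as changes, for example "Baseline to day 3 change in IL-8 and IL-6 concentrations in plasma". Nothing says that the baseline value will be a covariate.
- **Deferral:** "A complete statistical analysis plan will be finalised prior to study completion". That later plan is not among the documents.

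**The concern.** Stratified randomisation balances the arms on the strata, so the treatment difference varies less from one randomisation to the next than simple randomisation would allow. A two-group test that ignores the strata still uses the larger variance. If centre or cause predicts VFDs, that test rejects too rarely under the null and gives up power. There is no excess of false positives.

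Two further weaknesses follow from the text. Choosing covariates by observed imbalance makes the adjusted result depend on chance and on the analyst's judgement of what counts as imbalance. And the Cox model probably does not provide an adjusted analysis of the primary outcome at all. Elsewhere in the plan Cox regression is used only for duration of ventilation with deaths censored, whereas the VFD definition scores death before weaning as 0. These are different estimands.

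For the cytokines, a plain comparison of change scores is less precise than an analysis of the day-3 value adjusted for baseline.

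**Working it through.** **Inputs from the documents.** Difference of 33% of an SD, equal to 3 VFDs; two-sided 0.05; 80% power with 282 patients; 324 after inflation; 340 enrolled (Power calculations and sample size). 25-30 ICUs (Patient screening). Day 1 counts as ventilated, so VFDs run from 0 to 27 (Determination of primary outcome).

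**Assumptions.** 1:1 allocation (the ratio is not stated). R², the share of VFD variance explained by centre and cause, is not given, so 0, 5, 10 and 20% are shown.

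**The plan's own figures.** With an effect of 1/3 SD, total N = 4 × ((1.96 + 0.8416)/(1/3))² = 282.6, which matches 282. At 141 per arm, SE = √(2/141) = 0.1191 SD, and power = Φ(0.3333/0.1191 − 1.96) = Φ(0.839) = 79.9%. Then 282 × 1.15 = 324.3 and 324 × 1.05 = 340.2. The plan's numbers are reproduced.

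**Formula, strata balanced by design, 141 per arm**

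- Actual size of the unadjusted test: 2 × (1 − Φ(1.96/√(1−R²)))
- Unadjusted power: Φ((1/3 − 1.96·SE)/(SE·√(1−R²)))
- Adjusted power: Φ((1/3)/(SE·√(1−R²)) − 1.96)

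Example, R² = 10%, √0.9 = 0.9487. Size: 1.96/0.9487 = 2.066, giving 3.9%. Unadjusted power: 0.839/0.9487 = 0.884, giving 81.2%. Adjusted power: 2.799/0.9487 − 1.96 = 0.990, giving 83.9%.

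| R² | Size, unadjusted | Power, unadjusted | Power, adjusted | Loss (points) |
|---|---|---|---|---|
| 0% | 5.0% | 79.9% | 79.9% | 0 |
| 5% | 4.4% | 80.5% | 81.9% | 1.4 |
| 10% | 3.9% | 81.2% | 83.9% | 2.7 |
| 20% | 2.8% | 82.6% | 87.9% | 5.3 |

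**Simulation with incomplete blocks.** 324 patients; 28 centres × 2 causes = 56 strata, so 324/56 ≈ 6 patients each. Assumed: block size 4, 30% indirect cause, stratum variance split equally between centre and cause, R² on the latent scale. The outcome is a latent normal value rounded and clipped to 0-27, with mean 13.4 and SD 9.1 (the plan implies 3/0.33 = 9.1). The unadjusted Wilcoxon test is compared with a regression on ranks with cause fixed and centre random. There were 10,000 runs per cell; Monte Carlo error is about 0.2 points for size and 0.4 for power.

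| R² | Size, Wilcoxon | Power, Wilcoxon | Power, adjusted | Loss (points, before rounding) |
|---|---|---|---|---|
| 0% | 4.9% | 82.0% | 82.2% | 0.1 |
| 5% | 4.2% | 82.8% | 84.1% | 1.3 |
| 10% | 4.1% | 83.6% | 85.8% | 2.2 |
| 20% | 3.4% | 84.3% | 89.2% | 4.9 |

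The adjusted test's size stayed at 4.7-5.0%. A separate, smaller simulation (3,000 runs, centre as fixed effects) gave power of 80.4 v 80.0% at R² = 0, 82.5 v 82.7% at 5%, 83.1 v 85.8% at 10% and 85.0 v 89.8% at 20%.

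**Cytokines.** With equal variances at both times and correlation r, change-score variance is proportional to 2(1−r) and baseline-adjusted variance to 1−r². The ratio is (1+r)/2. For r = 0.3, 0.5, 0.7 and 0.9 it is 0.65, 0.75, 0.85 and 0.95, so variance falls by 35, 25, 15 and 5%. The correlations are assumed.

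**The case against.** The strongest reply is that nothing here is invalid. An unadjusted rank test after stratified randomisation controls the type I error, and in every scenario its power stays at about the planned 80% or above. What is lost is a gain from an optional analysis. The size of that gain rests on an assumed R²; five points need centre and cause alone to explain 20% of the variance, and at 5% the smaller simulation shows only 0.2 points. No gain has been computed for further covariates such as PaO₂/FiO₂. The imbalance-triggered model is a sensitivity analysis and cannot change the primary result. A complete SAP is promised and could settle all of this. The Wilcoxon test also fits the 15% inflation.

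Most of this stands as a limit on weight. It does not remove the point. Nothing in the text commits the later SAP to use the strata or to name covariates. At R² = 0, adjustment made no detectable difference in either simulation beyond Monte Carlo error. A clipped normal outcome might understate deaths, but similar gains remained when a separate 25% death component was added. The protocol also gives reason to expect stratum effects: it supports stratifying by cause with a study of the influence of direct and indirect aetiology on outcome, and it leaves rescue therapy and neuromuscular blockade to site practice.

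**Conclusion.** The concern holds. Neither stratification factor enters any planned analysis, the primary VFD test has to be inferred, and the covariates of the only adjusted analysis in the main plan are left to observed imbalance. That this Cox analysis does not cover VFDs is probable rather than stated.

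The consequence is a conservative test and some forgone power: negligible to small if the strata explain 5% of variance or less, about 2-3 points at 10% and about 5 at 20%. The upper figure depends on a strong assumption about R². For the cytokines, the gain in variance is 5-35% over the assumed correlations. This is a matter of efficiency and pre-specification that should be corrected; it does not threaten validity, and the sample size need not rise.

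**What to change.** In the statistical section or the promised SAP:

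1. Name one primary VFD analysis that accounts for cause of ARDS as a fixed effect and for centre as a random effect or through a stratified rank test. With about 6 patients per centre-by-cause stratum, full stratification would be sparse, so state a rule for small centres. Covariate-adjusted ordinal or rank regression is one suitable choice among several. Keep the unadjusted Wilcoxon test as supportive.
2. Replace imbalance-triggered selection with a short fixed list of baseline covariates, for example PaO₂/FiO₂, APACHE II and age. APACHE II already contains age points, so say whether both are kept.
3. Name the outcome of any Cox sensitivity analysis.
4. Analyse day-3 IL-6 and IL-8 with the baseline value as a covariate. The same applies to static compliance, which is measured in both arms before the assigned strategy starts and again on day 3.

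The cost is wording only, since these variables are already collected. The small downside is a modelling assumption, such as proportional odds for an outcome in which death before weaning scores 0; the supportive Wilcoxon test covers that.
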